1 INTRODUCTION

This Statistical Analysis Plan (SAP) contains technical and detailed elaboration of the principal features of the analysis described in the protocol, and includes procedures for executing the statistical analysis to fulfil the objectives of the study.

The final SAP will be approved prior to the primary database hardlock.

Changes from the planned analyses in the final SAP that impact the statistical analyses will be documented in the Clinical Study Report (CSR).

2 STUDY OBJECTIVE(S) AND DESIGN

2.1 Study Objectives

Cohorts 1 to 8:

Primary Objective:

To determine the antitumor activity of enfortumab vedotin as measured by confirmed objective response rate (ORR) per Response Evaluation Criteria in Solid Tumors (RECIST) Version 1.1 by investigator assessment.

Secondary Objectives:

- To assess other measures of antitumor activity of enfortumab vedotin per RECIST Version 1.1 by investigator assessment
- To assess the overall survival (OS)
- To assess the safety and tolerability of enfortumab vedotin

Exploratory Objectives:

- To evaluate potential genomic and/or other biomarkers that may correlate with treatment outcome, including Nectin-4 expression
- To assess the pharmacokinetics of enfortumab vedotin and monomethyl auristatin E (MMAE)
- To assess the immunogenicity of enfortumab vedotin
- To evaluate the treatment effect of enfortumab vedotin on quality of life (QOL)
- To assess measures of antitumor activity of enfortumab vedotin per blinded independent central review (BICR)

Cohort 9:

Primary Objective:

To determine the antitumor activity of enfortumab vedotin in combination with pembrolizumab as measured by confirmed ORR per RECIST Version 1.1 by investigator assessment.

Secondary Objectives:

- To assess other measures of antitumor activity of enfortumab vedotin in combination with pembrolizumab per RECIST Version 1.1 by investigator assessment
- To assess the OS of enfortumab vedotin in combination with pembrolizumab
- To assess the safety and tolerability of enfortumab vedotin in combination with pembrolizumab

Exploratory Objectives:

- To evaluate potential genomic and/or other biomarkers that may correlate with treatment outcome, including Nectin-4 expression
- To assess the pharmacokinetics of enfortumab vedotin and MMAE
- To assess the immunogenicity of enfortumab vedotin
- To evaluate the treatment effect of enfortumab vedotin in combination with pembrolizumab on QOL
- To assess measures of antitumor activity of enfortumab vedotin in combination with pembrolizumab per RECIST Version 1.1 by BICR
- To assess measures of antitumor activity of enfortumab vedotin in combination with pembrolizumab per iRECIST by investigator assessment

2.2 Study Design

This is an open-label, multicenter, multicohort, phase 2 study designed to assess the antitumor activity and safety of enfortumab vedotin as a single agent (cohorts 1 to 8) and in combination with pembrolizumab (cohort 9) in adult subjects with locally advanced or metastatic malignant solid tumors. Approximately 40 subjects will be enrolled into each of the following cohorts.

Cohort 1: Hormone receptor positive/ human epidermal growth factor receptor 2-negative (HR+/HER2-) breast cancer; or

Cohort 2: Triple negative breast cancer (TNBC); or

Cohort 3: Squamous non-small cell lung cancer (Squamous NSCLC); or

Cohort 4: Non-squamous non-small cell lung cancer (Non-squamous NSCLC); or

Cohort 5: Head and neck cancer; or

Cohort 6: Gastric or gastroesophageal junction (GEJ) or esophageal cancer (reallocated to Cohort 7 or 8)

Cohort 7: Gastric adenocarcinoma or esophageal adenocarcinoma (EAC) or gastroesophageal junction (GEJ) adenocarcinoma

Cohort 8: Esophageal squamous cell carcinoma (ESCC)

Cohort 9: Previously untreated head and neck squamous cell carcinoma (HNSCC)

Subjects enrolled into Cohort 6 will be reallocated based on disease type and histology into Cohort 7 or 8.

For each cohort, one interim analysis is planned to assess the antitumor activity for that cohort. The interim analysis will be performed for a given cohort at the time when 20 subjects are evaluable for tumor response per investigator assessment following study treatment. A Bayesian optimal design for phase 2 (BOP2) [Zhou et al, 2017] is used to guide interim decision rule. For each cohort, based on the 2-stage BOP2 design, when the number of subjects with confirmed response (complete response [CR] and partial response [PR] per Response Evaluation Criteria in Solid Tumors [RECIST] Version 1.1) is less than the prespecified minimum number of responders at stage 1, the enrollment of the cohort may stop; otherwise, the enrollment will continue until the planned size of the cohort is reached.

For each subject, the study will consist of 3 periods: screening/baseline, treatment and follow-up.

Starting at cycle 1, subjects in cohorts 1 to 8 will receive enfortumab vedotin on days 1, 8, and 15 of every 28-day cycle until one of the treatment discontinuation criteria is met. Subjects in cohort 9 will receive enfortumab vedotin on days 1 and 8 and pembrolizumab on day 1 of each 21-day cycle until a discontinuation criteria is met.

For cohorts 1 to 8, Imaging scan and disease assessment will be performed at screening/baseline and repeated every 8 weeks (56 days \pm 7 days) from the first dose of study treatment throughout the study until the subject has radiologically-confirmed disease progression, initiates a new subsequent anticancer therapy, dies, withdraws consent, is lost to follow-up or the study closes, whichever occurs first. After 1 year on study treatment, the frequency of disease assessment will be reduced to every 12 weeks (84 days \pm 7 days). Subjects who discontinue study treatment for reasons other than radiologically-confirmed disease progression by RECIST Version 1.1 will enter into a post treatment follow-up period and continue to receive imaging scans every 8 weeks (56 days \pm 7 days) until the subject has radiologically-confirmed disease progression, initiates a new anticancer therapy, dies, withdraws consent, is lost to follow-up or the study closes, whichever occurs first.

In cohort 9, the first on-study imaging will be performed 9 weeks (63 days \pm 7 days) from the first dose of study treatment and then every 6 weeks (36 days \pm 7 days) throughout the study until the subject has radiologically-confirmed disease progression (iCPD per iRECIST), initiates a new subsequent anticancer therapy, dies, withdraws consent, is lost to follow-up or the study closes, whichever occurs first. After 18 months on study treatment, the frequency of disease assessment will be reduced to every 9 weeks (\pm 7 days). Subjects with unconfirmed progressive disease per iRECIST guidelines (iUPD) [Seymour et al, 2017] who are clinically stable may continue on study treatment until progression is confirmed by the investigator (confirmed progressive disease [iCPD]) at the next imaging assessment 6 weeks (\pm 7 days) after iUPD. Treatment with pembrolizumab will be discontinued once the subject has received a maximum of 35 administrations of pembrolizumab (approximately 2 years).

Subjects in cohort 9 who discontinue study treatment for reasons other than radiologically confirmed disease progression per iRECIST will enter into a post treatment follow-up period and have physical exams, ECOG and disease assessments every 6 weeks (\pm 7 days) up to 18 months after first dose, then every 9 weeks (\pm 7 days) until the subject has radiologically

confirmed disease progression per iRECIST as determined by the investigator, initiates a subsequent anticancer therapy, dies, withdraws consent, or the study closes. During study treatment, palliative radiotherapy on a nontarget lesion that is not progressing will not be considered a subsequent anticancer therapy; however, radiotherapy on any target lesion will be a subsequent anticancer therapy.

Copies of all imaging scans will be sent to the independent review facility in a timely manner. Central images may be read for a cohort after the minimum number of responders (confirmed ORR) at stage 1 based on the 2-stage BOP2 design are met per investigator assessment. Central images may also be read in certain circumstances as determined by the sponsor.

An end of treatment (EOT) visit will be performed within 7 days after the last dose of enfortumab vedotin or the decision to discontinue treatment, or prior to initiation of another anticancer therapy, whichever occurs earlier. This will be followed by a 30-day safety follow-up to be completed 30 days (+ 7-day window) from the last dose of enfortumab vedotin. The 30-day follow-up assessments should be completed prior to the initiation of another anticancer therapy.

Response (CR or PR) must be confirmed with a repeat imaging scan 4 weeks (28 days + 7-day window) after first response.

After radiologically-confirmed disease progression or initiation of subsequent anticancer therapy, whichever occurs first, subjects will be contacted every 12 weeks in the long-term follow-up period for survival status until death, withdrawal of consent, lost to follow-up or study closure, whichever occurs first.

Blood samples for pharmacokinetics and antitherapeutic antibodies (ATA) will be collected at protocol-specified time points. Validated assays will be used to measure the concentrations of enfortumab vedotin and MMAE in serum or plasma and to assess ATA. Samples for exploratory biomarkers will be collected at protocol-specified time points. Enfortumab vedotin biomarker assessments will not be used for subject selection.

Details of the schedule of clinical assessments are available in the protocol.

2.3 Randomization

This is an open-label non-randomized study. Subject enrollment and dispensation of enfortumab vedotin will be performed via the interactive response technology (IRT) system.

3 SAMPLE SIZE

The planned sample size for cohorts 1 to 8 is approximately 40 subjects in each cohort. Assuming the reference ORR for the 7 tumor types chosen for the study, ranges from 10% to 20%, and at least a 10% absolute increase in ORR is considered clinical meaningful improvement, the sample size of 40 subjects allows to have an 80% confidence interval of enfortumab vedotin ORR to exclude the reference ORR. The actual sample size for each cohort may be less than the planned sample size depending on the ORR analysis result at the

planned interim analysis. Per Bayesian optimal design for phase 2 (BOP2), the enrollment of a cohort maybe stopped after interim analysis.

The planned sample size for cohort 9 is 40 subjects. Assuming the reference ORR for cohort 9 is 20%, and at least a 25% absolute increase in ORR is considered clinical meaningful improvement for combination therapy, the sample size of 40 subjects allows a 92% power to detect a statistically significant difference at type 1 error rate of 1-sided 0.025. The actual sample size for cohort 9 may be less than the planned sample size depending on the ORR analysis result at the planned interim analysis. Per BOP2, the enrollment of a cohort maybe stopped after interim analysis.

4 ANALYSIS SETS

In accordance with International Conference on Harmonization (ICH) recommendations in guidelines E3 (1995) and E9 (1998), the following analysis sets will be used for the analyses.

The determination of whether subjects are included or excluded from the analysis sets will be made prior to database hardlock.

4.1 Full Analysis Set

The full analysis set (FAS) consists of all enrolled subjects who receive any amount of study drug. The FAS will be used for primary analyses on overall survival (OS) and progression-free survival (PFS), as well as summaries for demographic, baseline characteristics and patient reported outcomes (PRO).

4.2 Response Evaluable Set

The response evaluable set (RES) is a subset of the FAS. It consists of the FAS subjects who have measurable disease at baseline per investigator assessment and either have at least 2 postbaseline response assessments or are no longer in the follow-up of response at the time of analysis. The RES will be used for the primary analysis set for the response related efficacy analyses, i.e., ORR, duration of response (DOR) and disease control rate (DCR), as well as demographic and baseline characteristics.

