9.2.2 Response Evaluable Set

The response evaluable set (RES) is a subset of the FAS. It consists of the FAS subjects who have measurable disease at baseline per investigator assessment and have at least 2 postbaseline scans or no longer in the follow-up of response at the time of analysis. The RES is the primary analysis set for the response related efficacy analysis.

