5.2.5.1 Best Overall Response

BOR is determined based on all available timepoint tumor response data for a subject. Responses recorded after new anticancer therapy or PD will be excluded from BOR derivation.

BOR with Confirmation

Confirmation of CR or PR should occur at the subsequent assessment no less than 4 weeks following the initial assessment at which CR or PR is observed. BOR with confirmation will be derived according to below criteria per RECIST Version 1.1:

- If a subject has at least 2 CR and the first and the last CR dates are at least 28 days apart, then the BOR for this subject is confirmed CR.
- If a subject has PR and another CR/PR at least 28 days apart, then the BOR for this subject is confirmed PR.
- For those subjects who do not have confirmed CR or PR, if the subject has at least one tumor assessment record of CR/PR/SD which is at least 49 days after the first dose, then BOR is defined as SD.
- For subjects who do not have confirmed CR, confirmed PR, or SD, as defined above, but they have a tumor assessment of PD, their BOR is PD.
- Otherwise, BOR is defined as Not Evaluable (NE). For subjects without any postbaseline tumor assessment, BOR is defined as No Data (ND) which is a subcategory of NE.

BOR Regardless of Confirmation

The BOR regardless of confirmation for a subject is defined at the best timepoint tumor response in the order of CR, PR, SD, PD and NE. SD must be documented as present at least once at or after 49 days post first dose for BOR to be SD.

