6.4.1 Analysis of Primary Efficacy Endpoint

6.4.1.1 Primary Analysis for Primary Efficacy Endpoint

Confirmed ORR per RECIST Version 1.1 by investigator assessment will be calculated for each cohort. The corresponding 95% confidence interval will be constructed using the Clopper-Person method. The primary analysis set for confirmed ORR is the RES per investigator assessment.

ORR based on BOR regardless of the confirmation will also be calculated to evaluate the impact on ORR due to missing of confirmatory scans or PD after the initial response.

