6.8 Timing of Analyses

Interim analysis for each cohort will be conducted as specified in Section 6.7.

Primary analysis will be conducted for each cohort when all subjects in a cohort have had the opportunity to be followed for at least 6 months after the first dose of study drug. At the time of primary analysis for a cohort other than the last enrolling cohort, all data for that cohort up to data cutoff will be included. For the last enrolling cohort, the following data will be included:

- Efficacy data for the last enrolling cohort up to data cutoff date.
- Non-efficacy data for all subjects from all cohorts up to data cutoff date.

The final analysis of the study will be conducted when all subjects have discontinued from the study.

A Safety Monitoring Committee (SMC) will periodically monitor the study for safety and review study safety data for all cohorts. The details will be provided in the SMC charter.

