Missing		4	1	4	1	4	1	1

1 = Impute the date of the first dose; 2 = Impute the first of the month; 3 = Impute January 1 of the year; 4 = Impute January 1 of the stop year

The imputed dates will be used to determine whether an AE is/is not treatment emergent. Listings of AEs and concomitant medications will present the actual partial dates; imputed dates will not be shown.

Subjects who do not satisfy the criteria to be counted as responders or have insufficient data to determine or confirm a response per the RECIST guidelines (Version 1.1) will be considered as non-responders in the final analysis of response rates. No imputation of data will be done to determine individual subject response.

For continuous variables (e.g., clinical laboratory measurement, vital signs), subjects with missing baseline variable will be excluded from the analysis of change from baseline.

For all analyses other than pharmacokinetic analysis, all values will be included in the analyses. For analysis of pharmacokinetic data, only samples for which the time of sampling relative to the dose administration and the exact dose is known will be included.

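### At the primary analysis the RES still excludes treated subjects in response follow-up with fewer than two assessments, which can raise the primary ORR slightly but never lower it (minor)

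*SAP*

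**What the plan says.** SAP 4.2 builds the RES from FAS subjects who have measurable disease at baseline per the investigator and who "either have at least 2 postbaseline response assessments or are no longer in the follow-up of response at the time of analysis". Protocol 9.2.2 has the same rule in terms of scans: subjects must "have at least 2 postbaseline scans or no longer in the follow-up of response at the time of analysis". Neither section limits the condition to one analysis. SAP 6.7 uses the same set to trigger the interim at 20 RES subjects, and SAP 6.4.1.1 makes it the set for the primary endpoint: "The primary analysis set for confirmed ORR is the RES per investigator assessment".

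Four other provisions bear on the point:

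- **Timing.** SAP 6.8 sets the primary analysis of a cohort for when "all subjects in a cohort have had the opportunity to be followed for at least 6 months after the first dose of study drug".
- **Confirmation.** SAP 5.2.5.1 needs two dated responses. For PR: "If a subject has PR and another CR/PR at least 28 days apart, then the BOR for this subject is confirmed PR". For CR the condition begins: "If a subject has at least 2 CR and the first and the last CR dates are at least 28 days apart".
- **Missing response data.** SAP 6.9.2 says that subjects who do not meet the responder criteria or who "have insufficient data to determine or confirm a response per the RECIST guidelines (Version 1.1) will be considered as non-responders". The sentence goes on to tie this to the final analysis of response rates.
- **Second set.** SAP 6.4 and protocol 9.4 also run the efficacy analyses on the FAS, that is, all treated subjects.

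**The concern.** At the interim, the two-assessment condition keeps out recent enrollees who have not had time for a response to appear and be confirmed. At the primary analysis that reason has gone. A subject who is then still in response follow-up with 0 or 1 assessment has missed scheduled scans, and the condition takes that subject out of the denominator of the primary endpoint.

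Because nobody with fewer than two assessments can have a confirmed response, the exclusion has a known direction for ORR. An analysis set whose membership depends on post-baseline data, and which can remove only non-responders, is better avoided for a single-arm primary endpoint, even where few subjects are affected. At stake are the reported ORR and its Clopper-Pearson interval.

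**Working it through.** **1. The plan's own figures.** For cohort 9 (20% versus 45%, N = 40, at least 14 responders), the exact binomial gives power 92.5% and one-sided alpha 0.0194. With the interim rule (at least 5 of 20) they are 91.8% and 0.0187. The stated 92% is reproduced, and the stated 0.025 is respected. The stated λ values and Beta(p0, 1 − p0) priors return all the tabulated boundaries: 4/12, 3/10, 2/7 and 5/14.

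**2. Scans due by 6 months.** Six months is 6 × 30.4375 = 182.6 days. Latest in-window days for the first three scans:

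- Cohorts 1 to 8 (every 56 ± 7 days): 56k + 7 = 63, 119, 175.
- Cohort 9 (day 63, then every 42 days, ± 7; protocol 4.1): 70, 112, 154. SAP 2.2 prints 36 days beside six weeks; that would only bring the later scans forward.

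All three fall before day 182. Protocol 6.6.1 keeps the assessment schedule anchored to cycle 1 day 1 during dose interruptions. A subject with 0 or 1 assessment has therefore missed at least two of three.

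**3. Who is excluded.** Only a treated subject with measurable disease who is still in response follow-up and has fewer than two assessments. Subjects who progressed, died, withdrew or started new therapy are out of response follow-up, so they stay in the RES.

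**4. Direction for ORR.** With r confirmed responders among N subjects, of whom d are excluded, each excluded subject adds 0 to r. Hence r/(N − d) ≥ r/N, with equality if d = 0 (or r = 0).

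**5. Size.** The documents give no value for d. Assuming d = 0 to 3, with N = 40 and r at the final boundary:

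| r | d = 0 | d = 1 | d = 2 | d = 3 |
|---|---|---|---|---|
| 7 | 17.5% | 17.9% | 18.4% | 18.9% |
| 10 | 25.0% | 25.6% | 26.3% | 27.0% |
| 12 | 30.0% | 30.8% | 31.6% | 32.4% |
| 14 | 35.0% | 35.9% | 36.8% | 37.8% |
| 14, 95% lower limit | 20.6% | 21.2% | 21.8% | 22.5% |

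Each excluded subject adds about 0.4 to 1 percentage point. The count r, and hence the comparison with 7, 10, 12 or 14, is the same in every column.

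**6. The one primary analysis reported.** Protocol 2.4.1 gives cohort 5 as 46 enrolled, 1 CR + 10 PR, confirmed ORR 23.9% and DCR 56.5%. 11/46 = 23.9%, whereas 11/45 = 24.4%. 26/46 = 56.5%, and no whole number over 44, 45 or 47 gives 56.5%. The section does not name the analysis set, but the denominator equals everyone enrolled, which is consistent with d = 0.

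**7. DCR.** Under SAP 5.2.5.1, one CR, PR or SD at day 49 or later, without confirmation, gives a BOR of SD, which counts as disease control. Taking cohort 5's 26/46 = 56.5% as a hypothetical base, excluding one such subject gives 25/45 = 55.6%; excluding one subject without disease control gives 26/45 = 57.8%. The effect can go either way.

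**The case against.** The strongest case against acting is that the group is close to empty. To be excluded, a subject must be alive, free of progression, consenting and on no new therapy, yet have missed at least two of three scans. The usual worry about evaluable sets, that early failures drop out, does not arise because the RES keeps them. Cohort 5 shows no sign of an exclusion, and the FAS analysis would show any gap. All of this stands, and it limits the size. It does not give the condition a purpose at 6 months, and the RES result remains the primary one.

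A reader might go further in three ways that the documents do not support:

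- **That SAP 6.9.2 contradicts the RES.** Its non-responder rule is tied to the final analysis of response rates. SAP 6.8 places the study's final analysis after all subjects have discontinued, when the excluded group is empty and the two sections agree. What remains is that 6.9.2 does not clearly cover the primary analysis.
- **That the eventual ORR is overstated.** The direction holds only at a given data cut. An excluded subject has not progressed, and one with a single unconfirmed PR could still be confirmed later.
- **That the type I error is breached.** Protocol 9.11 continues enrolment to 40 evaluable subjects. If two excluded non-responders were replaced, so that 42 were treated against a boundary of 14, the cohort 9 two-stage error would be 0.0280 against 0.025. This needs both exclusions and replacement. The documents show neither, and cohort 5 is consistent with no exclusion.

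**Conclusion.** The point holds as a minor one. SAP 4.2 and protocol 9.2.2 carry a condition suited to the interim into the primary analysis, where it can remove only subjects who are not confirmed responders at that cut. The primary ORR and its confidence limits therefore rise or stay the same: by about 0.4 to 1 percentage point per excluded subject at the boundary counts, and by nothing if none is excluded. The number excluded (0 to 3 in the table) is an assumption; the only evidence, cohort 5, is consistent with none. The size also assumes 40 subjects and a responder count at the boundary. The decision against the minimum responder count is unaffected for a fixed set of responders. Nothing here shows that any reported result is biased, and the one-way direction does not extend to DCR.

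**What to change.** In SAP 4.2, apply the two-assessment condition at the interim only. Suggested sense for the rest: *at the primary analysis, the RES is all FAS subjects with measurable disease at baseline per the investigator; for ORR, any subject without a confirmed CR or PR at the data cutoff is a non-responder; for DCR, the BOR rules of Section 5.2.5.1 apply.* DCR needs its own clause because a blanket non-responder rule would wrongly count a subject with one qualifying SD assessment as lacking disease control. The sentence also settles what SAP 6.9.2 leaves unclear for the primary analysis.

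Align protocol 9.2.2 at its next amendment; the point does not justify a separate one, given the signatures and ethics review that protocol 12.1.3 requires.

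The cost is one sentence in the SAP, later matched in the protocol, and a reported ORR that may be slightly lower if any subject would have been excluded. If none would have been, as the cohort 5 figures suggest for that cohort, the result is the same.
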